Title of trial: Comparison of Duodenal Stenting vs Transpyloric and Duodenal Stenting for Malignant Obstruction

NCT #: NCT03125148

Date of Document: March 17, 2017

STUDY PROTOCOL

Title: Comparison of Duodenal Stenting vs Trans-pyloric and Duodenal Stenting for Malignant Obstruction

Principle Investigator: [name]

Primary Contact: [name]

Purpose:

Enteral self-expanding metal stents (SEMS) are routinely used to palliate malignant gastric outlet obstruction (pancreas cancer, duodenal cancer, gastric cancer and metastasis) in patients not fit for surgical bypass. The technical success in placing these stents approaches ~100% and many of these procedures can be performed in an outpatient setting. However, the functional success (patient's ability to eat after stenting) is much lower than the technical success. One of the major reasons for this discrepancy is these patients are on narcotics which are known to be associated with poor gastric motility. At the discretion of the endoscopist, FDA approved enteral stents are placed either completely within the duodenum bridging the obstruction or placed across the pyloric opening besides bridging the duodenal obstruction.

The significance of this study is to determine if trans-pyloric extension of an intra-duodenal stent facilitates better gastric emptying compared to an intra-duodenal stent without trans-pyloric extension.

Background:

No studies have shown whether duodenal stenting by itself or duodenal stenting with transpyloric extension is superior in patients with duodenal obstruction secondary to malignancy. In one study, refractory gastroparesis secondary to benign etiologies (idiopathic, diabetes, and post-surgical) was managed with endoscopic trans-pyloric stent placement. In this study, clinical response was observed in 75% of patients. There was a predominant response in the patient's symptoms of nausea and vomiting. Gastric emptying studies were done post-stenting which showed the mean 4-hours gastric emptying normalized in 6 patients and significantly improved in 5 patients. In light of the success of trans-pyloric stenting in the setting of refractory gastroparesis due to benign pathology, we hope to show the same level of effectiveness in the setting of malignancy for which these stents are approved by FDA.

Hypothesis:

Enteral self-expanding metal stents deployed across the malignant duodenal obstruction with trans-pyloric extension will facilitate better gastric emptying and thereby better symptom relief compared to enteral self-expanding metal stents deployed completely within the duodenum.

Aims/Objectives:

The objective of this study is to compare symptom relief and gastric emptying in the following two groups of patients with malignant gastric outlet obstruction who have enteral self-expanding metal stents deployed 1) across the malignant duodenal obstruction with trans-pyloric extension and 2) enteral self-expanding metal stents deployed completely with the duodenum without trans-pyloric extension

Recruitment Methods:

Inpatients and outpatients referred to the Gastroenterology service at Froedtert Hospital for placement of enteral stents for palliation of malignant duodenal obstruction will be recruited as per the below inclusion and exclusion criteria. These patients are generally directly referred to the advance endoscopy faculty or are referred through the GI consult service.

Inclusion Criteria

- · Confirmed diagnosis of cancer
- Evidence of a single small bowel obstruction
- Considered palliative (can be on narcotics, chemotherapy, and/or radiation therapy)
- Not a surgical candidate
- >18 years of age
- Able to give consent
- Eligible for endoscopy (medically fit)
- Able to traverse past obstruction with a guidewire

Exclusion Criteria

- <18 years of age
- Unable to give consent
- Pregnant
- Have evidence of multiple sites of obstruction in the small bowel
- Have evidence of duodenal obstruction secondary to gastric cancer
- Ineligible for endoscopy (due to comorbidities or acuity of illness)
- Unable to traverse past obstruction with a guidewire

Methods/Procedures:

This is a prospective chart review study. All the procedures are being done for clinical indications. Since patients will be randomized to group A or Group B as below, a consent form will be used.

- Prospectively enroll patients based on inclusion-exclusion criteria.
- Stent deployment completely intra-duodenal vs with trans-pyloric extension based on randomization.
- Computer-generated randomization will be conducted. We expect to randomize 20 patients each to either complete intra-duodenal stenting (Group A) or with trans-pyloric extension (Group B).

- Symptoms of gastric outlet obstruction: heartburn, chest pain, regurgitation, bloating, belching, fullness after meals and epigastric pain will be collected from chart review prior to the procedure and post procedure as recorded during follow-up clinic visits.
- Medical record review of post-stent deployment (24-48 hrs post-deployment to allow for full expansion of the stent) gastric emptying studies.
- Solid and liquid T1/2 will be compared between these 2 groups using statistical analysis.
- An interim statistically analysis will be performed to determine if we need to study more patients.

Statistics:

We plan to study 40 patients prospectively (20 in each arm) and then using statistical software, conduct an interim analysis to determine if more patients are required. Solid and liquid T1/2 times will be compared between 2 groups using an unpaired T-test.

Risks to Participants

Patient will incur no additional risks associated with extending a stent trans-pyloric as opposed to leaving the stent completely intra-duodenal. Both these approaches are currently being practiced without any studies showing one approach being better or worse than the other. Also, patient's private and confidential information may be breached in case the data is accessed by an unauthorized person. In order to deal with this risk of confidentiality, the following measures will be taken:

- Personal identifying information will be available only to [name] and authorized study staff who are officially part of the study.
- Additionally, any paper forms will be kept in a locked cabinet at the gastroenterology department at MCW where the PI and research team members have access to the computer. The computer is password protected and only research members will have access to it. Any paper forms will be kept in a locked cabinet in the GI department.
- Once the data is complete from MCW, the data will be stored in an excel spread sheet that is password protected. The data will be stored for the duration of the study and analysis, and once the study is completed, all the de-identified data will be stored for no more than 10 years.
- Only [name] and other authorized personnel will have access to the study folder.

Consent Process

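### Symptom relief is half of the objective, but the form omits eating, nausea and vomiting, leaves the symptom ratings undated, and no symptom comparison is named

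*Combined protocol and SAP*

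**What the plan says.** - **Aims/Objectives:** "The objective of this study is to compare symptom relief and gastric emptying in the following two groups". **Hypothesis:** trans-pyloric extension "will facilitate better gastric emptying and thereby better symptom relief compared to enteral self-expanding metal stents deployed completely within the duodenum".
- **Purpose** states a narrower goal: "The significance of this study is to determine if trans-pyloric extension of an intra-duodenal stent facilitates better gastric emptying". It also glosses functional success as eating: "ability to eat after stenting) is much lower than the technical success".
- **Background** reports that, in a study of trans-pyloric stenting for benign gastroparesis, the response was mainly in nausea and vomiting.
- **Methods/Procedures:** "Symptoms of gastric outlet obstruction: heartburn, chest pain, regurgitation, bloating, belching, fullness after meals and epigastric pain will be collected from chart review", taken "prior to the procedure and post procedure as recorded during follow-up clinic visits". The gastric emptying study, by contrast, has a window of 24 to 48 hours after stent placement.
- **Statistics:** "Solid and liquid T1/2 times will be compared between 2 groups using an unpaired T-test". No other test is named. After 20 patients per arm the plan is to "conduct an interim analysis to determine if more patients are required".
- **Appendix I:** section F lists the same seven symptoms, to be circled if present. Section I asks for better, same or worse on each of the seven. Sections G and H have a date field; section I has none.

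**The concern.** A randomised comparison of symptom relief needs the relevant symptoms on the form, a known assessment time, a rule that turns ratings into one outcome per patient, and a comparison between arms. The plan supplies a baseline, a source and a per-symptom rating, but not the rest. The symptom list also leaves out the three outcomes that the protocol's own rationale brings up.

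The item content matters most. An analysis plan can still be written before the data are examined. Items never abstracted may not be recoverable later where the chart notes are silent. The trial could then finish with a T1/2 result and little to say on whether patients ate better. With no lead symptom named, there would also be room to highlight whichever of seven ratings looked favourable.

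**Working it through.** **1. The plan's own figure.** The only sample-size figure is 40 patients, 20 per arm. It cannot be reproduced, because no error rate, power, effect size or variance is given. There is no symptom calculation to check, so the main check is a comparison of the text.

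**2. The two halves of the objective side by side.**

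| Element | Gastric emptying | Symptom relief |
|---|---|---|
| In the objective and hypothesis | Yes | Yes |
| Measure | Solid and liquid T1/2 | Seven ratings, no patient-level rule |
| Timing | 24 to 48 hours after stenting | Follow-up clinic visits, no day or window |
| Date on the form | Section H: yes | Section I: no |
| Between-arm test | Unpaired t-test | None named |

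**3. Counts.** Of the three outcomes raised in Purpose and Background (eating, nausea, vomiting), 0 of 3 are recorded. Of the seven listed symptoms, 0 of 7 have a named test. Regurgitation is listed, but Background names vomiting in its own right. The same seven items appear in Methods/Procedures and in sections F and I, so the gap does not look like a PDF reading error.

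**4. False positives if all seven symptoms were tested.** All inputs here are assumptions: two-sided 0.05, no true effect, 20 per arm, no lead item.

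- Independent tests at exact size: 1 − 0.95^7 = 1 − 0.698 = 0.302.
- Simulated Wilcoxon tests on worse/same/better (four assumed splits, correlation 0 to 0.6, symptom present at baseline in 60% or 100%, 8,000 runs): 0.229 to 0.309. A smaller repeat with other assumed splits (1,000 runs per scenario) gave 23% to 34%. The standard error per scenario is about √(0.30 × 0.70/1,000) = 0.014, so the top of that range is not clearly different from 31%.
- Wilcoxon tests at correlation 0.8: about 18% to 25%.
- Fisher's exact test on better versus not better: about 12% to 20% at correlation 0 or 0.6, and about 10% to 16% at 0.8.

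The documents name no test and give no correlation, so the supportable range is about 10% to 31%.

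**5. What 20 per arm can resolve (illustration).** Assume one yes/no relief outcome, 50% against 75%, two-sided 0.05. The mean proportion is 0.625. The null standard error is √(2 × 0.625 × 0.375/20) = 0.153, and the alternative standard error is √((0.25 + 0.1875)/20) = 0.148. Power is Φ((0.25 − 1.96 × 0.153)/0.148) = Φ(−0.34), about 37%. Exact Fisher power is 27%. The interim look may raise the sample size, but by how much is not stated.

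**The case against.** The strongest reply is that this is a small study built on chart review whose stated significance is gastric emptying. The hypothesis places symptom relief downstream of emptying, and purely descriptive symptom reporting would fit the text. Eating appears in a sentence explaining why functional success lags technical success; it is not declared a trial outcome. Nausea and vomiting come from a different, benign condition. On this view, which symptoms to collect is partly a matter of preference.

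Much of this stands, and it limits what may be inferred:

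- A reader might infer that the plan carries a false-positive rate near 30%. It does not. No symptom test is specified, so no symptom error rate is being spent, and nothing shows that the item, visit or test will be picked after the data are seen. The 10–31% applies only if all seven are tested.
- A reader might infer that any blank item on the form is ambiguous. A symptom circled in F but left blank in I is simply unrated, because ‘same’ is available. The ambiguity is confined to section F and to symptoms not circled there.
- A fixed window cannot create records in a chart review; it loses those that fall outside it. That is a real cost of one version of the fix.

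What does not stand is the idea that the narrower significance statement removes the problem. The objective still names symptom relief, and the hypothesis still makes a directional claim about it. Patients are enrolled and randomised prospectively, so the form can be settled before data are collected.

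**Conclusion.** The point holds as a cheap improvement. The missing window, relief rule and test are mostly missing detail. The list and the form are the firmer problem: followed as written, they cannot show an effect on eating, nausea or vomiting, and the form alone cannot show whether the two arms were rated at similar times.

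These conclusions rest on the text alone. The 10–31% figure and the power illustration rest on assumed tests, splits, correlations and relief rates, none of which the documents give.

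A reader might go further and conclude that the trial's main comparison is compromised. The documents do not support that: the T1/2 analysis has its own measure, timing and test, and it matches the stated significance.

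**What to change.** 1. Add nausea, vomiting and a graded oral-intake item to the Methods/Procedures list and to form sections F and I, abstracted from the same chart notes.
2. Add an assessment date to section I, and a not-documented option in section F and for the items in section I.
3. In Statistics, pre-name one symptom outcome, secondary to T1/2. Oral-intake grade is one option; a pre-stated summary of the seven listed symptoms is another. Take it at a pre-stated visit: for example the first follow-up clinic visit with its date recorded, or the visit nearest a day that the sponsor chooses. Compare arms as randomised with a rank-based or ordinal test, using the baseline grade if the outcome is graded, and report the estimate with a 95% confidence interval. If the seven-symptom summary is chosen, state how patients with no baseline symptom are scored.
4. Report the other symptoms descriptively. Do not read a non-significant symptom result as equivalence. Limit any conclusion drawn from T1/2 alone to gastric emptying.

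**Cost:** seven form entries (three items in each of two sections, 3 × 2 = 6, plus one date), the not-documented options and one analysis paragraph; no extra visit or procedure. The downsides are slightly longer chart abstraction, missing grades where notes are silent or no clinic visit occurs, loss of records outside any fixed window, and modest power at 20 per arm.

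### Stent position is randomised, but the data form has no line for a complication or death, and the one planned look, after 40 patients, serves only to decide sample size

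*Combined protocol and SAP*

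**What the plan says.** **The interim look.** The Statistics section plans "40 patients prospectively (20 in each arm) and then using statistical software, conduct an interim analysis to determine if more patients are required". Methods/Procedures gives the same single purpose: "An interim statistically analysis will be performed to determine if we need to study more patients". The only between-group test named is an unpaired t-test on solid and liquid half-emptying times.

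**Risk.** Risks to Participants states: "Patient will incur no additional risks associated with extending a stent trans-pyloric as opposed to leaving the stent completely intra-duodenal". It then says: "Both these approaches are currently being practiced without any studies showing one approach being better or worse than the other". The other risk it names is a breach of privacy, and the protective steps are introduced with "In order to deal with this risk of confidentiality, the following measures will be taken".

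**What is collected by arm.** Aims/Objectives states: "The objective of this study is to compare symptom relief and gastric emptying in the following two groups of patients". Appendix I, sections A to I, records the randomised group, whether placement succeeded, whether the stent was fully expanded within 48 hours, the gastric emptying results, and seven symptoms rated Better, Same or Worse. Methods/Procedures takes the later symptom data "post procedure as recorded during follow-up clinic visits". No section of the form has a line for a complication, a re-intervention or a death.

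**Clinical setting.** Purpose describes current practice: "At the discretion of the endoscopist, FDA approved enteral stents are placed either completely within the duodenum bridging the obstruction", or extended across the pylorus. Methods/Procedures describes a prospective chart review of clinically indicated procedures, with stent position set by randomisation.

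**The concern.** Outside the trial the endoscopist chooses the stent position; inside it, the allocation does. The patients are receiving palliative care and are not surgical candidates. The protocol states that the two positions carry equal risk, and the sentence that follows reports only that no study separates them. Absence of comparative studies does not establish equal risk. A randomised comparison is well placed to describe any difference, but this one does not plan to record the most serious outcomes.

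The stake is patient safety. If one position led to more serious complications, the team could report the trial, or decide to randomise more patients, without having counted those events by arm. The decision on extension is the one point at which the plan already stops to look at data.

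**Working it through.** **Step 1. Is the omission real?** The plan's items compare as follows.

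| Item | Recorded on the form? | By-arm comparison planned? |
|---|---|---|
| Half-emptying times | Yes (section H) | Yes, t-test |
| Seven symptoms, including worsening | Yes (section I) | Yes, as an objective; no test named |
| Placement success, full expansion | Yes (section G) | Not stated, but possible |
| Complication | No | No |
| Death | No | No |

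The symptom ratings depend on attended clinic visits. A patient who dies early or is too ill to attend could have no rating. That is an inference; the documents do not discuss it.

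**Step 2. The plan's own figure.** The only figure is 40 patients, 20 per arm. It cannot be reproduced, because no alpha, power, effect size, standard deviation or event rate is given. All rates below are therefore assumptions.

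**Step 3. Would an arm see any events?** With true rate p, the chance of at least one event in 20 is 1 - (1 - p)^20.
- p = 5%: 1 - 0.95^20 = 64%
- p = 10%: 1 - 0.90^20 = 88%
- p = 20%: 1 - 0.80^20 = 99%

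**Step 4. What would a by-arm count show?** Let X and Y be independent binomial counts with n = 20 each. Each probability is the sum of P(X = x)P(Y = y) over the pairs (x, y) concerned.

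Equal true rates, so any difference is chance:

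| Rate in both arms | Counts differ | Differ by 2 or more | Differ by 4 or more |
|---|---|---|---|
| 5% | 69% | 25% | 1.3% |
| 10% | 79% | 42% | 6% |
| 15% | 82% | 50% | 12% |
| 20% | 84% | 55% | 16% |

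Unequal true rates:

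| Rates | Worse arm ahead by 4 or more |
|---|---|
| 5% v 10% | 7% |
| 5% v 15% | 21% |
| 10% v 20% | 25% |
| 10% v 30% | 58% |
| 10% v 40% | 84% |

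A lead of 4 is only a yardstick here, not a proposed rule.

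**Step 5. Could equal counts show equal harm?** Use Newcombe's 95% interval, built from the Wilson limits (l, u) of each arm. When both arms have the same count it is ±√[(p - l)² + (u - p)²].
- 2/20 in each arm: the Wilson limits are 0.028 and 0.301. The interval is ±√[(0.100 - 0.028)² + (0.301 - 0.100)²] = ±0.214, or about -21 to +21 percentage points.
- 0/20 in each arm: the Wilson upper limit is 0.161, so the interval is about -16 to +16 points.
- 2/20 v 6/20: by the general form, about -5 to +43 points.

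So the table would usually expose a very large difference, would often miss a moderate one, and could not establish equal safety.

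**The case against.** The strongest case against has three parts.

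**The form does carry some harm information.** A reader might infer that the trial would have no harm data by arm at all. The documents do not support that. The form has the randomised group, placement success, expansion, and a Worse option for each symptom, including chest pain and epigastric pain, and symptom comparison is a stated objective. This part stands, and it confines the point to complications and deaths. The reliance on clinic visits makes the symptom data possibly incomplete, not absent.

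**The setting limits the danger.** Both positions are existing practice with approved stents, the procedures are clinically indicated, and one centre's team would probably know of serious events in its own patients. Events would presumably be in the charts, so an arm count could be made later, and the investigator or ethics board could act outside the plan. This stands as a limit on weight. What is missing is a commitment to make the count; awareness of individual events is not a tabulation by randomised group.

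**Twenty per arm is too few to guide a decision.** This is largely right for moderate differences: at 10% v 20% the worse arm leads by 4 or more in only 25% of trials. The larger contrasts, where the table performs well, are assumed rates that nothing in the documents supports. That argues for a descriptive table without a trigger. It does not argue for leaving the events unrecorded.

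**Conclusion.** The point holds in a limited form. Appendix I has no complication or death line, the sole interim look has only a sample-size purpose, and the statement of no added risk has no comparative evidence behind it in the documents. Followed as written, the trial could end at 40 or continue past it with those events uncounted by arm.

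A reader might also infer that one position is more dangerous, or that patients go without clinical oversight. The documents show neither: they give no complication rates, and clinical care runs outside this plan.

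The size of any harm difference is unknown. The value of recording events is moderate: a large difference would usually become visible, while equal counts would still leave roughly ±16 to ±21 points of uncertainty. These figures assume 20 evaluable patients per arm, independent events, and the illustrative rates shown. This is a change that should be made because it is cheap and it alters what the trial can say about safety.

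**What to change.** **Add two lines to Appendix I:**
- *Serious stent- or procedure-related complication within the window: Yes / No, type, date.*
- *Death from any cause within the window: Yes / No, date, judged related Yes / No.*

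The investigators should set the qualifying events and the window in advance (for example 30 days). Deaths need their own line because in palliative cancer patients deaths from the disease could otherwise dominate a combined count.

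**Add to Statistics:**

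> *Complications and deaths will be tabulated separately by randomised group, with the number randomised, the number stented, and the number followed to the end of the window or to death. This descriptive table will be produced before any decision to enrol beyond 40 and again at the end of the study, including if enrolment stops at 40.*

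No numerical trigger is proposed. The change governs trial conduct and does not direct any patient's care.

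**Cost.** Two form lines, one event definition, two sentences, and a slightly wider review of up to 40 charts by the existing team. It needs no new committee, procedure or patients. An extension could be delayed by up to one window after the last patient if the team waits for every window to close; the follow-up column lets it proceed sooner with the gap visible. The other downside is over-reading chance: at an assumed 10% in both arms the counts would differ in 79% of trials, so the table should be labelled descriptive.

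### The 40-patient interim look decides whether to enrol more, but with no extension rule, alpha, maximum N, number of looks or adjustment stated, the plan does not control type I error

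*Combined protocol and SAP*

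**What the plan says.** Methods/Procedures expects 20 patients to be randomized to each of Groups A and B. The same section then says "An interim statistically analysis will be performed to determine if we need to study more patients". The Statistics section repeats this for the 40-patient sample: "20 in each arm) and then using statistical software, conduct an interim analysis to determine if more patients are required". So 40 is both the expected sample and the point at which the final sample size is decided.

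The T1/2 comparison is listed as a separate item in Methods/Procedures: "Solid and liquid T1/2 will be compared between these 2 groups using statistical analysis". Statistics names the method: "Solid and liquid T1/2 times will be compared between 2 groups using an unpaired T-test". No other inferential method appears in the document.

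The document does not state:
- what quantity is examined at the interim, or whether the arms are compared;
- what result leads to more enrolment;
- alpha or sidedness;
- a target difference, SD or power;
- the maximum N or the number of looks;
- any adjustment of the final test.

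The interim sentences are complete and carry no redaction marks.

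**The concern.** When accumating data decide whether a trial continues, the final test keeps its nominal level only under some decision rules. If the arms are compared at 40 patients, a significant result is accepted, and a non-significant one leads to more patients and an unadjusted retest, a false difference has two or more chances to appear. If the look uses no arm comparison, or permits no efficacy claim, the level holds.

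The plan allows both kinds of rule and commits to neither. If enrolment passes 40, a reader of the protocol could not tell whether the reported p-value keeps its nominal level. A rule chosen after the arms have been seen would not repair that. At stake is the trial's one formal comparison, of T1/2 between stent positions.

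**Working it through.** **Inputs.** From the document: 20 per arm at the interim, 1:1 allocation, unpaired t-test. Assumed, because the document is silent: two-sided 0.05 at each test, one T1/2 outcome at a time, and one extension from 20 to n2 per arm, with n2 from 22 to 80. The 40-patient figure cannot be reproduced, since no difference, SD, alpha or power is given.

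**One extension, success allowed at 20 per arm.** Under no difference, the interim statistic Z1 and final statistic Z2 are standard normal with correlation √(20/n2). Then

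type I error = 0.05 + 2 × ∫ φ(z) · P(|Z2| ≥ 1.96 | Z1 = z) dz,

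with the integral over the positive z values that lead to extension. Given Z1 = z, Z2 has mean z√(20/n2) and variance 1 − 20/n2. For n2 = 40 the correlation is √0.5 = 0.707; extending every non-significant result adds 3.31 points, giving 8.31%.

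| n2 per arm | extend if p 0.05–0.10 | extend if p 0.05–0.20 | extend if p ≥ 0.05 |
|---|---|---|---|
| 22 | 6.04% | 6.38% | 6.41% |
| 25 | 6.07% | 6.79% | 7.09% |
| 30 | 5.97% | 6.89% | 7.70% |
| 40 | 5.82% | 6.76% | 8.31% |
| 60 | 5.64% | 6.49% | 8.83% |
| 80 | 5.55% | 6.33% | 9.07% |

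Simulated t-tests agree to within about 0.1 point.

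**More than one extension.** Unadjusted t-tests at 20, 40 and 60 per arm give about 10.8%; adding a look at 80 gives about 12.6%. The table is therefore not an upper limit.

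**Rules that hold the level.**
- No claim at the interim and a fixed extension: 5.0%.
- Stop for futility at p > 0.5, with no interim claim: 5.0% falling to 3.7% as n2 goes from 22 to 80.
- Stopping at 40 as final: 5.0%.
- Re-estimation from the SD of all patients without labels: about 5.0% in simulation.

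Re-estimation from the within-arm SD, which needs labels, came out at about 5.1% to 5.5%.

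**What the label-free rule costs in patients.** For 80% power at two-sided 0.05, n per arm = 2 × (1.960 + 0.842)² × (SD/difference)² = 15.7 × (SD/difference)². With the within-arm SD this gives 15.7/0.75² = 27.9 and 15.7/0.65² = 37.2. The total SD also contains the arm difference: for a true difference of d SD, the total variance from 40 patients averages 1 + (40/39) × d²/4.
- d = 0.75: 27.9 × 1.144 = 31.9.
- d = 0.65: 37.2 × 1.108 = 41.2.

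Simulation with a cap of 60 per arm gives mean n of about 32 and 41, with power 81% and 80%. A cap of 40 gives about 78% power for 0.65 SD. For comparison, 20 per arm has 80% power only for about 0.91 SD (noncentral t), 64% for 0.75 SD and 52% for 0.65 SD.

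**The case against.** The strongest reply is that the plan never says the arms are tested at 40. The look has one stated purpose, deciding whether more patients are needed. Stopping for efficacy is not mentioned, and the T1/2 comparison is listed apart from the interim. It could be a variance check, or enrolment could simply end at 40. In those cases nothing is inflated.

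This stands as far as it goes. A reader might infer that the plan commits to a t-test at 40 and a second one after an extension, with error of 7% to 9%. The text does not support that. Nor does it support treating 9% as a ceiling, since neither a maximum N nor a number of looks is given.

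It does not remove the concern. A variance check needs a target difference to say whether more patients are required, and none is stated. Appendix I records randomization group and T1/2 on the same data sheet, and nothing keeps the analyst blind to group, so an arm-blind look would need an explicit instruction. The document does not call the trial a pilot: its Hypothesis section predicts better emptying with trans-pyloric extension.

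**Conclusion.** The omission is certain: the total sample size depends on an interim look with no stated rule, and the only named test carries no adjustment. The supported conclusion is that type I error is left uncontrolled, not that it is necessarily inflated. The percentages are illustrations per outcome at an assumed two-sided 0.05, and the table also assumes a single extension and a success claim allowed at 20 per arm. On those terms the error is about 5.6% to 6.9% for near-miss extension and 6.4% to 9.1% for extension after any non-significant look. It is higher with further looks, and about 5% or less where the look involves no arm comparison or no efficacy claim. This should be fixed. Testing both solid and liquid T1/2 is a separate multiplicity question and is not counted here.

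**What to change.** Before any arm comparison, amend the Statistics paragraph to adopt one of these.

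(a) Label-free re-estimation, the closest to the stated purpose. At 20 per arm, compute the total (one-sample) SD of T1/2 across all patients, from a file with group labels removed. Set n per arm = 15.7 × (SD/target difference)², with the target difference and a maximum N stated now. Enrol to the smaller of n and the maximum, never below 20. Make no arm comparison at the interim, and run one final t-test at two-sided 0.05. State which T1/2 supplies the SD, or take the larger n.

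(b) Declare the 40-patient analysis final and delete the word interim.

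(c) If the arms are to be compared at the interim, fix the maximum N and use a two-look boundary. For equal spacing, use O'Brien-Fleming (0.0052, then 0.0480) or Pocock (0.0294 at each look); otherwise use alpha spending.

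**Cost.** Each option is one paragraph of wording. Option (a) also needs someone to strip labels from the interim file, gives up any early efficacy claim, and requires the sponsor to choose a target difference and cap; the recruitment it implies is shown in the working. If those numbers cannot be recruited, (b) is simplest, but detects only large differences. For looks at 20 and 40 per arm, (c) reduces power from 80% to 79.7% with O'Brien-Fleming or 75.6% with Pocock.
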